Subject recruitment for this study will be through advertisement in local newspapers and through postings of the included flyers in various public places such as, but not limited to, libraries, public universities, hospitals, health clubs, and local health fairs. Additionally, advertisements may be placed in some national newspapers or websites (Craigslist) to reach a wider audience, particularly for the lean, weight-maintaining arm of the study. We aim to recruit 50% women for each study arm. A review of previous enrollment in our studies indicates that we typically have an even distribution of ethnic groups in our study samples (e.g. control versus treatment) even when the representation of ethnic categories is not equal. Thus, we expect to have at least 33% of volunteers represented by African American, Hispanic, Asian, or Native American groups in each of our study arms. We plan to enroll 60 individuals and in order to enroll this many, we will likely need to screen many more. We have therefore set our anticipated number to be screened at 180, equal to three times the number enrolled. For randomization, we will stratify the groups by gender and age, using a block design.

2. Inclusion Criteria:

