The design of this study will allow us to look at differences in levels of adherence to a heart-healthy dietary prescription in lean vs. obese individuals. We will also be able to compare adherence levels in obese individuals who are being fed a WMEN diet compared to an UF diet. Additionally, we will measure predictors of adherence and the relationship between adherence and weight loss.

Data Analysis:

Measuring Adherence: (see Appendix B): for all measures, adherence will be examined as a binary variable (adherent versus non-adherent). Each measure will be awarded 0 points if non-adherent and 1 point if adherent.

1. Attendance: two sessions per week: (adherent = attended; non-adherent = not attended; 12 possible total points over the study).
 - a. counseling
 - b. food pick-up
2. Food Diaries: volunteers will turn in diaries during their weekly counseling visit. For each weekly diary there will be three scores (18 possible total points over the study):
 - a. *Completion of records*: adherent = completed diary; non-adherent = missing or incomplete diaries
 - b. *Dietary Adherence to Foods provided*: adherent = consumed all; non-adherent = did not consume all
 - c. *Adherence to Additional Foods*: adherent = did not consume any; non-adherent = consumed additional foods
3. 24-hour recall in-person interview: once per week on day of counseling session. For each session there will be three scores (18 possible total points over the study):
 - a. *Completion of interview*: adherent = completed interview; non-adherent = did not complete interview
 - b. *Dietary Adherence to Foods provided*: adherent = consumed all; non-adherent = did not consume all
 - c. *Adherence to Additional Foods*: adherent = did not consume any; non-adherent = consumed additional foods

4. 24-hour recall using computerized confessional: once per week on day of counseling session. For each session there will be three scores (18 possible total points over the study):
 - a. *Completion of records*: adherent = completed interview; non-adherent = did not complete interview
 - b. *Dietary Adherence to Foods provided*: adherent = consumed all; non-adherent = did not consume all
 - c. *Adherence to Additional Foods*: adherent = did not consume any; non-adherent = consumed additional foods
5. 24-hour recall (telephone): once per week. For each phone session there will be three scores (18 possible total points)

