 - a. *Completion of recall*: adherent = completed recall; non-adherent = did not complete recall
 - b. *Dietary Adherence to Foods provided*: adherent = consumed all; non-adherent = did not consume all
 - c. *Adherence to Additional Foods*: adherent = did not consume any; non-adherent = consumed additional foods
6. EMA recordings: there will be two contacts per day. For each contact there will be three adherence scores. To avoid having EMA be more heavily weighted in the total score, the total weekly score will be divided by 7 to obtain an average weekly EMA score (42 possible total points per week; 6 possible total average points):

- a. *Completion of recording*: adherent = completed recording; non-adherent = did not complete recording. We will define incomplete or missing entries as non-adherent for that day.
 - b. *Dietary Adherence to Foods provided*: adherent = consumed all; non-adherent = did not consume all
 - c. *Adherence to Additional Foods*: adherent = did not consume any; non-adherent = consumed additional foods
7. Additional Non-Intervention Related Adherence Measure (once per week. For each rating there will be 1 score (6 possible total points over the study): We will also track the arrival time for weekly counseling session as a measure of adherence that is not directly related to the study intervention. Appointment adherence will be scored as the arrival within 5 minutes of the scheduled time and actual arrival time will be documented as a continuous measure of adherence. This measurement will allow us to examine the relationship between adherence to the dietary protocol and adherence to "other" factors (e.g. punctuality) and it will be included in the total adherence score.
- a. Appointment adherence: adherent = arrived within 5 minutes of scheduled appointment; non-adherent = did not arrive within 5 minutes of scheduled appointment

Adherence Score: The above variables will be totaled up to calculate a total adherence score out of a possible 21 points during each week. A percent (%) adherence score will also be calculated by dividing the total score by the number of variables assessed (21) and multiplying by 100 ($[(\text{total}/21)*100]$).

Statistical Analysis:

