adherence observed in the POUNDS LOST study by an additional 10% and applied this increase in score across all 3 groups. Thus, assuming 62% adherence, we would expect a mean weekly score of 13 in the calorie restricted group. If we in addition, consider a smaller a meaningful difference between the groups of 3 points; (lean WMEN = 19, obese WMEN = 16, obese UF = 13), assuming the same SD = 6, with a calculated sum of squares of the means = 32, across 3 treatment groups with a mean 16 +/- SD = 6, alpha = 0.05, the proposed total of 20 subjects per group (total n = 60) would allow us to achieve a power of 0.793 (**see table 3a**). If we assume a larger difference between the groups 3.5 points; lean WMEN = 20, obese WMEN = 16.5, obese UF = 13), the proposed total of 20 subjects per group (total n = 60) would allow us to achieve a power of 0.906 (**see Table 3a**). Because the drop-out rate in weight loss intervention studies averages around 25%, we plan to recruit a total of 150 subjects (25 per group) to account for both screening failures and attrition, and to ensure 60 completers (**see Table 3b**).

7. Benefits:

This is a supervised dietary outpatient study being offered to lean and overweight/obese individuals. The prescribed diet is "Heart-healthy" and could improve metabolic and health outcomes in all 3 groups. In addition, those in the UF group who adhere to the diet may experience weight loss, which may lead to additional favorable future metabolic outcomes. All volunteers will receive information regarding some aspects of their health, including lab screening tests, a thorough physical examination, a measure of body fat, and an evaluation of their glucose tolerance status. The results of these tests will be available to the subjects and will be provided to their personal physician, if desired. Other expected benefits of this study include obtaining generalizable knowledge related to the difference in levels of adherence between lean

and overweight/obese individuals, which has not yet been examined. We will also gain knowledge about predictors of treatment adherence for weight loss and the relationship between adherence and weight loss. Moreover, we are proposing novel ways to measure adherence, which could be used in future studies. The information obtained from this study should be useful to scientists, physicians, and psychologists.

8. Human Subjects Precautions:

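### The recruitment figures (60, 75, 150 and 180) do not reconcile, and at 25% drop-out neither 60 nor 75 enrolled supports the promised 60 completers

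*Combined protocol and SAP*

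**What the plan says.** Section D.1 (Subjects and Recruitment) fixes enrolment at 60: "We plan to enroll 60 individuals and in order to enroll this many, we will likely need to screen many more". It sets the "anticipated number to be screened at 180, equal to three times the number enrolled".

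Section D.6 (Power Calculation) treats 60 as the number on which power rests: "the proposed total of 20 subjects per group (total n = 60) would allow us to achieve a power of 0.793", for mean weekly scores of 19, 16 and 13 and an SD of 6. It then allows for losses. "Because the drop-out rate in weight loss intervention studies averages around 25" per cent, it says, "we plan to recruit a total of 150 subjects (25 per group) to account for both screening failures and attrition", "and to ensure 60 completers". Table 3b is cited for that last statement.

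Section 8.1 (Recruitment and Minority Participation) expects about 5 volunteers a month for about a year and a half. The Statistical Analysis paragraph keeps in the final analysis all who finish the run-in, and fills in missing data by multiple imputation.

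**The concern.** The design has three groups, so the total and the per-group figure in the same sentence of section D.6 do not match each other. Nor does either match section D.1. Staff working from section D.1 would stop at 60 enrolled, and staff working from section D.6 would stop at 25 per group. Nothing in the document says which governs.

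The second problem is the allowance for drop-out. The plan sets its own target in completers and names its own drop-out rate, but neither enrolment figure meets that target at that rate. At stake are how many people are enrolled, when recruitment stops, and whether the power of 0.793 describes the trial that will be run.

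**Working it through.** **Inputs.** From section D.6: three groups, means 13/16/19 (alternative 13/16.5/20), SD 6, alpha 0.05, 20 per group, drop-out about 25%, 25 per group, 150 in total, 60 completers. From section D.1: 60 enrolled, 180 screened. From section 8.1: about 5 a month for about 18 months.

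**1. The plan's own power.** The overall F test of a one-way ANOVA has noncentrality n × SS / SD², where SS is the sum of squared deviations of the group means from their average, with 2 and 3n − 3 degrees of freedom.
- For 13/16/19, SS = 9 + 0 + 9 = 18. At n = 20 the noncentrality is 20 × 18/36 = 10 and the power is 0.793, as stated.
- For 13/16.5/20, SS = 12.25 + 0 + 12.25 = 24.5. At n = 20 the power is 0.906, as stated.

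Both powers are correct for 60 analysed. The sum of squares printed in the text, 32, is not the 18 that these means give, but the printed power does not depend on that slip.

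**2. The total.** 3 × 25 = 75. A total of 150 would be 50 per group (150/3), or six groups of 25 (150/25).

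**3. Against section D.1.** If 150 is a pool before screening and 75 enter, half fail screening. Section D.1 has 180 screened for 60 enrolled, so two thirds fail. Pool and enrolment both differ. Section 8.1 gives 5 × 18 = 90, but does not say whether recruiting there means screening or enrolling.

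**4. The drop-out allowance.** The 25 per group equals 20 × 1.25. To be left with 20 after losing 25%, one needs 20/0.75 = 26.7, so 27 per group (81). In total, 60/0.75 = 80.

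**5. Completers at 25% drop-out** (binomial, independent drop-outs, the same rate in every group):

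| Enrolled | Expected completers | Chance of at least 60 |
|---|---|---|
| 60 | 45 | 0.000 |
| 75 | 56.25 | 0.195 |
| 80 | 60 | 0.560 |
| 81 | 60.75 | 0.633 |

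Seventy-five enrolled would give an expected 60 only at 20% drop-out (75 × 0.80 = 60).

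**6. Power for 13/16/19, SD 6,** using the formula in step 1. Completers are taken to have the same means and SD.

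| Enrolled | Completers only, 25% drop-out | All contribute full data |
|---|---|---|
| 60 | 15 per group: 0.654 | 20 per group: 0.793 |
| 75 | 18.75 per group on average: 0.764 | 25 per group: 0.883 |

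For 13/16.5/20 the same four cells are 0.794 and 0.906 (60 enrolled), and 0.885 and 0.960 (75 enrolled).

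**The case against.** **The 150 was never meant to equal 3 × 25.** The sentence mentions screening failures as well as attrition, so 150 may be the pool before screening and 25 per group the number entering. This is plausible and would explain 150 against 75. The text does not say it, though, and the reading still leaves 150 against 180 screened and 75 against 60 enrolled. It does nothing for the completer target.

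**Completers do not determine power here.** The planned analysis is by intention to treat with multiple imputation, so the number analysed need not be the number of completers. This stands, and it is why the completers-only powers are the lower end of a range and not a forecast. It does not rescue the completer target, which the sponsor set itself. Imputation also does not restore full information, so 0.88 and 0.79 are upper ends.

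**The 25% may be too high.** It comes from weight-loss studies, and only one of the three groups is underfed. That is fair. It is still the only rate the plan gives, and at 20% the expected number from 75 is exactly 60, which is not a guarantee.

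**Stronger readings.** A reader might infer that each group must keep 20 completers and judge the plan against that. The plan promises 60 in total and sets no per-group criterion, and the F test does not need exactly 20 in each. A reader might also infer a severe loss of power because missed items count as zero: "adherent = completed diary; non-adherent = missing or incomplete diaries" for diaries and "We will define incomplete or missing entries as non-adherent for that day" for the phone recordings. Those rules cover missed items and do not mention people who have withdrawn, while the analysis paragraph imputes missing data. The size and direction of any effect would also depend on drop-out rates by group, which the documents do not give. How a drop-out is scored deserves its own point and carries no weight here.

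**Conclusion.** The recruitment figures are wrong as written and should be corrected. Sections D.1 and D.6 give enrolment and screening numbers that cannot both hold. At the plan's own 25% drop-out, 60 enrolled fall about 15 short of 60 completers and 75 enrolled about 4 short, so the promise of 60 completers is unsupported on either figure.

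The documents do not support going further and calling the trial seriously underpowered. The 0.793 is right for 60 analysed. At 75 enrolled the worst case considered costs about 3 points of power and the best gains about 9. At 60 enrolled the loss could reach about 14 points (0.793 − 0.654). The planned analysis falls somewhere within these ranges if imputation is used for drop-outs. This rests on 25% drop-out in every group and on the plan's means and SD.

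**What to change.** State one enrolment number and one screening number, say what each counts, and use them in sections D.1, D.6 and 8.1.

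If 25 per group is kept, section D.6 should state 75 enrolled and about 56 expected completers at 25% drop-out. It should give power of about 0.76 (completers only) to at most 0.88 (all contribute full data), replace 150 with the sponsor's own screening number, and remove the promise of 60 completers. Section 8.1 should say whether its monthly rate refers to people screened or enrolled.

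If the sponsor prefers to keep 60 as the expected number of completers, enrolment has to be 80, or 81 with equal groups. The wording should then be that 60 are expected, since the chance of reaching 60 with 81 enrolled is only 0.633.

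In the same edit, replace the sum of squares 32 with 18, cite Table 3B for 0.906, and remove the Table 3b citation from the completer statement, because that table holds only the 13/16.5/20 power run. None of these changes a result.

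Cost: keeping 25 per group is a change of wording, with nobody added relative to section D.6 and 15 more enrolled than in section D.1. The 81 option enrols 6 more than 75 and 21 more than section D.1. Screening numbers would have to follow.

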8.1. Recruitment and Minority Participation

Participants will be recruited via advertising in local newspapers and on the internet, strategies which have proved successful in the past. Based on our previous studies, we expect the ethnic diversity of our volunteers to be approximately 40% Caucasian, 40% Native American, 10% Black and 10% Hispanic. Native Americans represent approximately 2% of the population in greater Phoenix area, and we anticipate over-representation because our unit is situated within the Phoenix Indian Medical Center. Additionally, Native Americans have previously participated in many of our studies. We anticipate recruiting approximately 5 volunteers per month (60/year) over the course of about 1.5 years.

8.2. Safeguards for subjects:

Subjects will have the option of discontinuing the study at any time. All data will be treated confidentially, and the identity of subjects will not be disclosed in publications. Participants will be monitored (weight and blood pressure) and seen by a counselor weekly. Any participant judged on clinical grounds to have suffered any adverse effect will be evaluated by a provider (physician, physician assistant, nurse practitioner, or psychologist).

8.3. Risks and Discomforts:

8.3.a Radiation exposure due to DXA: The DXA scans will take place on the GE Lunar iDXA machine. The radiation exposure for a 188 mA scan may be as much as 1 mrem as indicated by a January 2014 internal radiation exposure review. According to the manufacturer, the medium and fast scan speeds are likely to result in one-half the radiation exposure of the slow scan speed. A typical radiation dosage from this procedure is equivalent to 1.22 days (iDXA) of exposure to natural background sources, such as the sun and outer space, or radioactive materials found naturally within the earth's air and soil. For subjects who move excessively during the scans, a complete or partial repeat of the scan procedure may be necessary. Thus, subjects could receive a maximum of 2 mrem (iDXA, 2.5 days of exposure) if the slow scanning mode is used each time. Participants in this study will undergo 2 DXA scans over the study period therefore the maximum amount of radiation they will receive in the first year could be as high as 4 mrem (iDXA, 5 days of exposure). This exposure increases the percent cancer risk from 25 percent to 25.00016 (iDXA). This is well within the NIH Phoenix Radiation Safety Guidelines for research subjects of 3,000 mrem in a 13-week period and 5,000 mrem per year. A urine pregnancy test will be performed in all females who are able to become pregnant prior to each DXA scan.

8.3.e Dietary Intervention: The side-effects of consuming a pre-selected diet are minimal and might include boredom, lack of desire to eat the prescribed foods and/or increased feelings of hunger.

8.3.e Questionnaires and computer performance tests: There are no known risks associated with completing any of these questionnaires. However, some of the questions may be of a highly personal nature; thus, subjects will be informed that they do not have to respond to all the questions if they choose not to do so. If this is the case, notations to that effect will be noted in the patient's record.

8.3.f Urine Drug Screen: Results of this test will be used only to determine study eligibility. If the result is positive, patients will be confidentially informed of the results and a recommendation for follow-up will be made with their primary physician.

8.3.g Blood Withdrawal: The amount of blood that may be drawn from adult patients and volunteers (i.e., those persons 18 years of age or older) for research purposes shall not exceed 10.5 mL/kg or 550 mL, whichever is smaller, over any eight week period.

8.3.h Adherence Measurements: Receiving phone calls from study staff and completing EMA assessments and food records could be perceived as a nuisance, but there are no known risks. Recalling food eaten, associated moods and related activities could induce negative emotions but the risks are minimal.

8.4. Disclosure of medical conditions:

The participants will be informed of any medical conditions uncovered by the screening blood work performed and referred to their primary care provider. The information will also be entered into their medical records and, at the patient's request, sent to their physicians. In the event that during screening, participants are found to have psychotic symptoms and present a danger to themselves or others, behavioral health services (available on site in the facility) will be contacted for appropriate referrals. All information from the study will be made available to the patients and their physicians at the patients' request. Information will be treated with the same protection and confidentiality as all other medical records. All information from the study may be made available to insurance companies if the information is requested by the insurance company and the subject signs a release of information. This could affect future insurability and employment opportunities.

8.5. Data and Safety Monitoring:

8.5. a. Independent Data Safety Monitoring Board: Potential adverse events from this study are expected to be infrequent. Therefore, the principal investigator (PI) will act as the safety monitor and report these events to the NIDDK IRB. Study procedures will be subject to audits and/or monitoring visits to ensure compliance with the protocol and applicable regulatory requirements consistent with the PIMC quality assurance program plan. Audit and/or monitoring visits results will be reported to the Principal Investigator for further reporting as appropriate. Study documents and pertinent hospital or clinical records will be reviewed to verify that the conduct of the study is consistent with the protocol plan.

8.5.b. Adverse events, protocol deviations, unanticipated problems (UP), serious adverse events, are defined as described in NIH HRPP SOP 16 (“Reporting Requirements for Unanticipated Problems, Adverse Events and Protocol Deviations”). All adverse events occurring during the study, including those observed by or reported to the research team, will be recorded and assessed for relatedness to the study procedures or treatments, severity and whether or not they are expected (in nature, severity and frequency). Serious unanticipated problems and serious protocol deviations will be reported to the IRB and Clinical Director (CD) as soon as possible but not more than 7 days after the PI first learns of the event. Non-serious unanticipated problems will be reported to the IRB and CD as soon as possible but not more than 14 days after the PI first learns of the event. Non-serious protocol deviations will be reported to the IRB as soon as possible but not more than 14 days after the PI first learns of the event. Non-serious protocol deviations that result from the normal subject scheduling variations or technical issues associated with sampling that does not impact the health of the subject or the interpretation of the study data will not be reported. Deaths will be reported to the CD and the IRB within 7 days after the PI first learns of the event. Previously undiagnosed medical conditions discovered by laboratory testing or imaging will not be reported

as adverse events, but will receive appropriate follow-up and referral to the primary care provider.

- The PI is responsible for summarizing all adverse events at least possibly related to the research procedure and interventions at the time of Continuing Review. All deaths that have occurred among study participants since the previous review will be summarized at the time of continuing review.

8.6. Research Use of Stored Human Samples, Specimens or Data:

